1	Time since MM diagnosis	Time (in months) from first MM diagnosis to index date (continuous)	MM diagnosis to index date

Objective	Variable	Definition	Assessment Period(s)
1	Triple class exposed	
Medical claim in the IP, Non-IP or pharmacy setting with an NDC, HCPCS, Current Procedural Terminology (CPT), generic name, or ICD-10 procedure code for all the following therapies in the IP, non-IP, or pharmacy setting (dichotomous)¹⁶:
 
 • ≥ 1 claim for PIs (see generic names below) • ≥ 1 claim for IMiDs (see generic names below) • ≥ 1 claim for CD38 mAbs (generic names: daratumumab, isatuximab) 	MM diagnosis to 1 day prior to index date
1	Penta-drug exposed	
Medical claims with an NDC, HCPCS, CPT, generic name, or ICD-10 procedure codes in the IP, non-IP or pharmacy setting for all of the following therapies (dichotomous)¹⁶:
 
 • ≥ 2 distinct claims for PIs (see generic names below) • ≥ 2 distinct claims for IMiDs (see generic names below) • ≥ 1 claim for CD38 mAbs (generic names: daratumumab, isatuximab) 	MM diagnosis to 1 day prior to index date
1	Hematopoietic Stem Cell Transplantation ¹	
Medical claim with an HCPCS, CPT, or ICD-10 code for hematopoietic stem cell transplantation in the IP, non-IP setting (dichotomous)
	
MM diagnosis to 1 day prior to index date
 
Index date to the end of follow-up

1	BCMA-directed therapy ¹	
Medical claim with an NDC, HCPCS CPT, generic name or ICD-10 procedure code in the IP, non-IP, or pharmacy setting for idecabtagene vicleucel, ciltacabtagene autoleucel, or belantamab (dichotomous)
	
MM diagnosis to 1 day prior to index date
 
Index date to the end of follow-up

1	CAR-T ¹	
Medical claim with an NDC, HCPCS, generic name or CPT code in the IP, non-IP, or pharmacy setting for idecabtagene vicleucel or
	
MM diagnosis to 1 day prior to index date

Objective	Variable	Definition	Assessment Period(s)
		ciltacabtagene autoleucel (dichotomous)	Index date to the end of follow-up
1	Talquetamab ¹	Medical claim with an NDC, HCPCS, generic name or CPT code in the IP, non-IP, or pharmacy setting for talquetamab (dichotomous)	MM diagnosis to 1 day prior to index date Index date to the end of follow-up

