1	PIs ¹	Medical claim with an NDC, HCPCS, generic name or CPT code in the IP, non-IP, or pharmacy setting for bortezomib, carfilzomib, or ixazomib (dichotomous)	MM diagnosis to 1 day prior to index date Index date to the end of follow-up
1	IMiDs ¹	Medical claim with an NDC code or generic name in the non-IP or pharmacy setting for lenalidomide, thalidomide, or pomalidomide (dichotomous)	MM diagnosis to 1 day prior to index date Index date to the end of follow-up
1	Steroids ¹	Medical claim with an NDC, HCPCS, generic name or CPT code in the IP, non-IP, or pharmacy setting for dexamethasone, methylprednisolone, prednisone, or prednisolone (dichotomous)	MM diagnosis to 1 day prior to index date Index date to the end of follow-up
1	MAbs ¹	Medical claim with an NDC, HCPCS, generic name or CPT code in the IP, non-IP, or pharmacy setting for daratumumab, isatuximab, or elotuzumab (dichotomous)	MM diagnosis to 1 day prior to index date Index date to the end of follow-up
1	Chemotherapies ¹	Medical claim with an NDC, HCPCS, generic name or CPT code in the IP, non-IP, or pharmacy setting for	MM diagnosis to 1 day prior to index date

Objective	Variable	Definition	Assessment Period(s)
		doxorubicin hydrochloride, melphalan, bendamustine, cyclophosphamide, etoposide, or cisplatin (dichotomous)	Index date to the end of follow-up
1	Small molecule inhibitors ¹	Medical claim with an NDC, HCPCS, generic name or CPT code in the IP, non-IP, or pharmacy setting for venetoclax (dichotomous)	MM diagnosis to 1 day before index date Index date to the end of follow-up
1	Nuclear export inhibitors ¹	Medical claim with an NDC, HCPCS, generic name or CPT code in the IP, non-IP, or pharmacy setting for selinexor (dichotomous)	MM diagnosis to 1 day before index date Index date to the end of follow-up
1	Antivirals ¹	Medical claim with an NDC, HCPCS, generic name or CPT code in the IP, non-IP, or pharmacy setting for antiviral medications (dichotomous)	14 days prior to index date to 1 day prior to index date Index date to the end of follow-up
1	Antibiotics ¹	Medical claim with an NDC, HCPCS, generic name or CPT code in the IP, non-IP, or pharmacy setting for antibiotic medications (dichotomous)	14 days prior to index date to 1 day prior to index date Index date to the end of follow-up

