1	Serum immunoglobulin E (IgE)	Lab event with IGE as the test name and IU/mL as the result units (dichotomous)	180 days prior to index date to index date
		Most recent numeric value of a lab event with IGE as the test name and IU/mL as the result units (continuous)	
1	Serum immunoglobulin M (IgM)	Lab event with IGM as the test name and mg/dL as the result units (dichotomous)	180 days prior to index date to index date
		Most recent numeric value of a lab event with IGM as the test name and mg/dL as the result units (continuous)	
1	Bone marrow plasma cell percent	Lab event with bone marrow plasma cell percent as the test name and percent as the result units (dichotomous)	Most recent value recorded in the 180 days prior to index date to index date
		Most recent numeric value of a lab event with bone marrow plasma cell	

Objective	Variable	Definition	Assessment Period(s)
		percent as the test name and percent as the result units (continuous)	
1	M-Protein	Lab event with M-Spike as the test name and as the g/dL as the result units (dichotomous)	180 days prior to index date to index date
		Most recent numeric value of a lab event with M-Spike as the test name and g/dL as the result units (continuous)	

1. Variable assessed both at baseline and in follow-up

Table 3 includes definitions and assessment periods for all study variables being used as outcomes. The full code list can be found in ANNEX 2. ADDITIONAL INFORMATION. If applicable, the frequency and percentage of patients with missing data for each variable will be described.

Table 3. Key Variables of Interest

Objective	Variable	Definition	Assessment Period(s)
Treatment exposure			
2	Use of premedication	
Medical or pharmacy claim with evidence of an NDC, HCPCS, generic name or CPT code for the following premedications (dichotomous):
 
Acetaminophen
 
Dexamethasone
 
Diphenhydramine
	
Step-Up Dosing Period
 
See Section 9.7.2 for censoring criteria

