ANNEX 2. ADDITIONAL INFORMATION

Variable	Role	Data Source(s)	Codes	Source
Elranatamab	Inclusion criteria	Claims data	HCPCS: C9165, J1323 NDC: 00069449401, 00069449402, 00069252201, 00069252202 ICD-10 Procedure code: XW013L9 Generic name: Elranatamab	ELREXFIO Outpatient Billing (2024) ELREXFIO Inpatient Billing (2024)
Teclistamab	Inclusion criteria (Exploratory cohort)	Claims data	HCPCS (Mapped via SEER using generic name): J9380, C9148 NDC: 57894044901, 57894045001 ICD-10 Procedure code: XW01348 Generic name: Teclistamab	Janssen Biotech (2023) SEER (2024)
Multiple Myeloma	Inclusion criteria, Outcome - HCRU	Claims data	C90.0x	ELREXFIO Outpatient Billing (2024)
Age	Inclusion criteria, Baseline characteristic - Demographic	Claims data	N/A	N/A
Sex	Baseline characteristic - Demographic	Claims data	N/A	N/A
Race/Ethnicity	Baseline characteristic - Demographic	Claims data	N/A	N/A

PFIZER CONFIDENTIAL

Redacted

Insurance type	Baseline characteristic - Demographic	Claims data	N/A	
Care setting	Baseline characteristic - Clinical	Claims data	See rows below: "Inpatient," "Outpatient," and "Emergency Department"	N/A
Hematopoietic stem cell transplantation	Baseline characteristic - Treatments	Claims data	
CPT: 38240, 38241, 38242, 38243
 
ICD-10 Diagnosis: T86.0, T86.00, T86.01, T86.02, T86.03, T86.09, T86.5, Z48.290, Z94.81
 
ICD-10 Procedure: 30240Y0, 30243Y0, 30250Y0, 30253Y0, 30260Y0, 30263Y0, 30230Y1, 30233Y1, 30240Y1, 30243Y1, 30230Y2, 30233Y2, 30240Y2, 30243Y2, 30230Y3, 30233Y3, 30240Y3, 30243Y3, 30230Y4, 30233Y4, 30240Y4, 30243Y4, 30253Y1, 30260Y1, 30263Y1, 30233X0, 30233G0, 30233G1, 30233G2, 30233G3, 30233X1, 30233X2, 30233X3, 30233X4, 30233Y0, 30243X0, 30243G0, 30243G1, 30243G2, 30243G3, 30243X1, 30243X2, 30243X3, 30243X4, 0243Y4, 30283X0, 30283G0, 30283G1, 30283G2, 30283G3, 30283X1, 30283X2, 30283X3, 30283X4, 30283Y1, 30283Y2, 30283Y3, 30283Y4
	
Chaudhry et al. (2022)
 
LeMaistre et al. (2013)

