Steroids	Baseline characteristic - Treatments, Outcome - HCRU	Claims data	HCPCS (Mapped via SEER using generic name): J8540, J1100, J1094, J7509, J1040, J1030, J1020, J2930, J2920, J7510, J2650, J7512, J7506, J1010, J2919 Generic names (Mapped to NDC codes via First Data Bank): Dexamethasone, Methylprednisolone, Prednisone, Prednisolone* *Prednisolone is not listed in NCCN	Usmani et al. 2016 NCCN (2024) SEER (2024)
CD38 mAbs	Baseline characteristic - Treatments, Outcome - HCRU	Claims data	HCPCS (Mapped via SEER using generic name): J9415, C9476, J9227, J9144, C9062 NDC (Mapped via SEER using generic name): 57894050301, 00024065401, 00024065601, 57894050205, 57894050220, 57894050505, 57894050520 Generic names: Daratumumab, Isatuximab	NCCN (2024) Gozzetti et al. 2022
mAbs	Baseline characteristic - Treatments, Outcome - HCRU	Claims data	HCPCS (Mapped via SEER using generic name): J9415, C9476, J9227, J9144, C9062, C9477, J9176 NDC (Mapped via SEER using generic name): 57894050301, 00024065401, 00024065601, 57894050205, 57894050220, 57894050505, 57894050520, 00003229111, 00003452211 Generic names: Daratumumab, Isatuximab, Elotuzumab	SEER (2024) NCCN (2024) Wudhikarn et al. 2020
Chemotherapies	Baseline characteristic - Treatments, Outcome - HCRU	Claims data	HCPCS (Mapped via SEER using generic name): C9243, J9033, J9034, J9060, J9062, C9418, J9091, J9070, J9092, J9080, J9090, C9420, C9421, J9093, J9094, J9095, J9096, J9097, J8530, J9100, C9422, J9110, J9098, J9000, C9415, J9002, Q2048, Q2049, Q2050, J9001, J9181, J9182, C9425,	Cowan et al. (2022) NCCN (2024)

PFIZER CONFIDENTIAL

Redacted

			
J8560, C9414, J9245, J8600, J8610, J9250, J9260, J9036, J9246, C9080, C9024, J9247, C9087, J9071, J9056, J9058, J9059, J9072, J9255, J9073, J9074, J9075, J9248, J9249, J8611, J8612
 
Generic names (Mapped via SEER using generic name): Melphalan, Bendamustine, Cyclophosphamide, Doxorubicin, Etoposide, Cisplatin, Methotrexate*, Cytarabine*
 
*Methotrexate and cytarabine are not in NCCN; however, they have been used in the treatment of multiple myeloma with central nervous system relapse
	SEER (2024)
Small molecule inhibitors	Baseline characteristic - Treatments, Outcome - HCRU	Claims data	
NDC (Mapped via SEER using generic name): 00074057611, 00074057622, 00074057630, 00074057634, 00074057928, 00074056111, 00074056114, 00074056607, 00074056611
 
Generic name: Venetoclax
	SEER (2024) NCCN (2024)

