Lymphocyte count	Baseline characteristic - Lab	Claims data	An event in the lab results table where the result_abbrev is lymphocytes count and result_units are thousand per µL	
Monocyte count	Baseline characteristic - Lab	Claims data	An event in the lab results table where the result_abbrev is monocytes count and result_units are thousand per µL	
Platelet Count	Baseline characteristic - Lab	Claims data	An event in the lab results table where the result_abbrev is platelets and result_units are thousand per µL	
ImmunoglobulinA	Baseline characteristic - Lab	Claims data	An event in the lab results table where the result_abbrev is IGA and result_units are mg per dL	
ImmunoglobulinG	Baseline characteristic - Lab	Claims data	An event in the lab results table where the result_abbrev is IGG and result_units are mg per dL	
ImmunoglobulinE	Baseline characteristic - Lab	Claims data	An event in the lab results table where the result_abbrev is IGE and result_units are IU per mL	
ImmunoglobulinM	Baseline characteristic - Lab	Claims data	An event in the lab results table where the result_abbrev is IGM and result_units are mg per dL	
Bone marrow plasma cell percent	Baseline characteristic - Lab	Claims data	An event in the GDD table where the test is bone_marrow and result_units are percent	
M-Protein	Baseline characteristic - Lab	Claims data	An event in the GDD table where the test is m-spike and result_units are mg/dL	
Use of premedication	Outcome - Dosing and Administration Patterns	Claims data	HCPSCS (Mapped via SEER [Dexamethasone only] or Athena – OHDSI using generic name): J0136, J0137, J0134, J0131, C9283, G6039, J1200, Q0163, J8540, J1100, J1094	SEER (2024) ELREXFIO Label

PFIZER CONFIDENTIAL

Redacted

			Generic names (and associated NDCs): Acetaminophen, Dexamethasone, Diphenhydramine	
Inpatient	Baseline characteristic, Outcome - HCRU	Claims data	Any event in the inpatient table or an event in the non-inpatient table where acute_subacute is “acute inpatient” or where utilization type is “professional services” and service subcategory contains the term “hospital/ip encounter”	
OP	Baseline characteristic, Outcome - HCRU	Claims data	Any event in the non-inpatient table where utilization type is outpatient and service subcategory is not “emergency dept encounter”	
ED	Baseline characteristic, Outcome - HCRU	Claims data	Any event in the non-inpatient table where utilization type is “outpatient” and service subcategory is “emergency dept encounter”	

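### The follow-up stem cell transplant variable also counts diagnosis codes that mark an existing transplant, so transplants done before index can be reported as done after it

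*Protocol*

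**What the plan says.** Protocol section 9.3, Table 2, defines the transplant variable under Objective 1 as "Medical claim with an HCPCS, CPT, or ICD-10 code for hematopoietic stem cell transplantation in the IP, non-IP setting (dichotomous"). Any one qualifying claim sets it to yes. Two assessment windows are given: from myeloma diagnosis to the day before index, and "Index date to the end of follow-up". The row carries footnote 1, "Variable assessed both at baseline and in follow-up".

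Annex 2 holds the only code list for this variable. It has three parts: four CPT codes (38240 to 38243), a long set of ICD-10 procedure codes, and the diagnosis set "ICD-10 Diagnosis: T86.0, T86.00, T86.01, T86.02, T86.03, T86.09, T86.5, Z48.290, Z94.81". Neither Table 2 nor Annex 2 limits the follow-up assessment to part of the list, asks for a procedure code, or asks for an event that is new since index. Under section 9.2.1 the teclistamab cohort follows the same rules, apart from the drug that sets the index date.

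**The concern.** The two windows ask different questions. The baseline window asks whether the patient has ever had a transplant, and evidence of an existing transplant answers that. The follow-up window asks whether a transplant took place after the index drug was started, and only evidence that dates the transplant answers that. One list cannot serve both questions if some of its codes say only that a transplant happened at some time.

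At stake is a percentage reported under a primary objective, in each cohort and at each data refresh. The study is descriptive, so no later model corrects the figure. A visible share of patients apparently transplanted after a bispecific antibody would be a notable clinical statement, and a reader of the table could not tell that it came from status codes.

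**Working it through.** The protocol gives no figure for follow-up transplant, so there is nothing to reproduce. The check sets the definition against the code list.

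**Step 1: what each part of the list shows.** Annex 2 itself separates diagnosis from procedure codes but prints no labels. On the standard ICD-10-CM meanings:

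| Codes in Annex 2 | Number | What a claim shows | Dates a transplant? |
|---|---|---|---|
| CPT 38240 to 38243 | 4 | the procedure | yes |
| ICD-10 procedure codes | many | the procedure | yes |
| T86.0, T86.00 to T86.03, T86.09, T86.5 | 7 | complication of a transplant | no |
| Z48.290 | 1 | aftercare | no |
| Z94.81 | 1 | transplant status | no |

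The diagnosis part therefore has 7 + 1 + 1 = 9 codes.

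**Step 2: apply the rule to three patients.**

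- Patient A was transplanted before index, with the procedure captured, and has one Z94.81 claim at a visit after index. As written: baseline yes, follow-up yes. With procedure codes only in follow-up: baseline yes, follow-up no.
- Patient B was transplanted before the data begin (1 January 2016) or outside captured claims, and the only trace is a status code after index. As written: baseline no, follow-up yes, which looks like a first transplant after the index drug. Cross-tabulating the two rows would not reveal this.
- Patient C has a CPT transplant claim after index. Follow-up is yes under either rule.

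The definition cannot separate A and B from C.

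**Step 3: is there a safeguard elsewhere?** For most adverse events, Table 3 separates incident from prevalent cases with washouts of 14, 30 or 60 days. Transplant has no such rule.

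**Step 4: possible size, for illustration only.** Let t be the true share transplanted after index, p the share with a prior transplant, and c the chance that such a patient has at least one of the nine diagnosis codes on a claim in follow-up. Then

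reported share = t + (1 − t) × p × c.

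The protocol gives none of these. With assumed values and t = 0:

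| p | c | Reported share | Of 56 patients |
|---|---|---|---|
| 0.20 | 0.25 | 0.20 × 0.25 = 5% | 2.8 |
| 0.40 | 0.50 | 0.40 × 0.50 = 20% | 11.2 |
| 0.60 | 0.90 | 0.60 × 0.90 = 54% | 30.2 |

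With t = 2% and the middle row, the reported share is 0.02 + 0.98 × 0.20 = 21.6%. The 56 is the count of patients with an elranatamab claim in section 9.5; it only gives scale and is not the size of the eligible cohort.

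**Step 5: where the variable is used.** The next-treatment list behind TTD, TTNT/D and the censoring rules in sections 9.7.2, 9.7.5 and 9.7.6 consists of CAR-T, bispecific antibodies, belantamab and bendamustine. OS depends on death alone. Transplant enters none of these.

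**The case against.** **Annex 2 gives the list a baseline role only.** One could say the list was never meant for follow-up. This does not hold: antivirals, antibiotics and antifungals carry the same baseline-only role in Annex 2, and Table 2 assesses them in follow-up too. Table 2 and its footnote are explicit for transplant, and no other list exists.

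**The code meanings are not in the protocol.** This is correct. Reading the nine codes as complication, aftercare and status rests on standard ICD-10-CM. The protocol shows only that they are diagnosis codes, kept apart from procedure codes. A complication code could also follow a transplant performed after index, but the definition cannot tell the two cases apart.

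**Section 9.9 already discloses misclassification.** It covers rule-out and erroneous coding. Here the code is accurate and the window is wrong, which is a matter of definition that the analyst can correct.

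**The stakes are small.** This stands in part. One descriptive row per cohort is affected, in a study without formal comparisons.

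A reader might also infer that the steroid row has the same fault. It covers "pharmacy setting for dexamethasone, methylprednisolone, prednisone, or prednisolone (dichotomous") from the index date, dexamethasone is also listed in Table 3 as step-up premedication, and the HCPCS codes J8540, J1100 and J1094 appear in both Annex 2 lists. The overlap is real, but it is not an error. A dexamethasone claim after index is a true steroid exposure after index. The same footnoted group of rows also holds antivirals, antibiotics, antifungals and immunoglobulin, so it is not confined to myeloma therapy. Table 3 reports premedication in a row of its own. Whether to take step-up steroids out is a matter of preference.

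**Conclusion.** The point holds for transplant alone. Followed as written, the protocol counts some transplants performed before index as transplants performed after it, and the follow-up percentage is inflated in both cohorts. This rests on the standard meaning of the nine diagnosis codes and on at least some previously transplanted patients having such a claim after index.

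The size cannot be derived from the protocol. The 5% to 54% shown above follows from assumed inputs and is not an estimate. A reader might infer that the follow-up row mostly reproduces baseline history, but the protocol does not support that: genuine procedure codes count as well, and neither share is known. Nor does it support any effect on TTD, TTNT/D, OS or censoring. The change is worth making because it corrects a reported figure under a primary objective at little cost.

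**What to change.** In Table 2, split the transplant row by window. In follow-up, count only CPT 38240 to 38243 and the ICD-10 procedure codes of Annex 2 dated on or after index. At baseline, keep the full list, diagnosis codes included. In Annex 2, mark which codes serve which window and add the follow-up use to the role column.

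The cost is one code-list split and minor reprogramming. Version 2.0 is dated 31 July 2025, and the milestones place refreshes 3 and 4 and the final report after that date, so those outputs can carry the corrected row. If the results delivered before then used the full list in follow-up, a note should say that the row is not comparable. The one downside is that a new transplant recorded only through a diagnosis code would be missed. To show how much the choice matters, the number of patients with only a diagnosis code in follow-up can be given in a footnote.

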1	Antifungal Medication ¹	Medical claim with an NDC, HCPCS, generic name or CPT code in the IP, non-IP, or pharmacy setting for antifungal medications (dichotomous)	14 days prior to index date to 1 day prior to index date Index date to the end of follow-up
1	Intravenous immunoglobulin ¹	Medical claim with an NDC, HCPCS, generic name, CPT, or ICD-10 procedure code in the IP, non-IP, or pharmacy setting for intravenous	14 days prior index date to 1 day prior to index date

Objective	Variable	Definition	Assessment Period(s)
		immunoglobulin administration (dichotomous)	Index date to the end of follow-up
1	Other hematological malignancies	Medical claim with an ICD-10 code in the IP or non-IP setting for hematological malignancies other than MM (dichotomous)	MM diagnosis to 1 day prior to index date
1	Any non-hematological malignancy	Medical claim with an ICD-10 code in the IP or non-IP setting for non-hematological malignancies (dichotomous)	MM diagnosis to 1 day prior to index date
1	Plasma cell leukemia	Medical claim with an ICD-10 code in the IP or non-IP setting for plasma cell leukemia (dichotomous)	MM diagnosis to 1 day prior to index date
1	Bone lesions	Medical claim with an ICD-10 code in the IP or non-IP setting for bone lesions (dichotomous)	MM diagnosis to 1 day prior to index date
1	Peripheral neuropathy	Medical claim with an ICD-10 code in the IP or non-IP setting for peripheral neuropathy (dichotomous)	MM diagnosis to 1 day prior to index date
1	Any infection	Medical claim with an ICD-10 code in the IP or non-IP setting for any infection of the following types (dichotomous): COVID-19 Sinusitis Bronchitis Adenoviral pneumonia Cytomegaloviral pneumonitis Other Pneumonia Upper respiratory tract infection	MM diagnosis to 1 day prior to index date

Objective	Variable	Definition	Assessment Period(s)
		
Sepsis
 
Cytomegaloviral infection
 
Pneumocystis jiroveci pneumonia (PJP)
 
Hepatitis C
 
Hepatitis B
 
Other infectious hepatitis
 
Helicobacter pylori
 
Candida esophagitis
 
Urinary tract infection
	
1	Use of intravenous anti-infective	Medical claim with an NDC code generic name, CPT, or HCPCS code in the IP, non-IP, or pharmacy setting for anti-infective where the route of administration is intravenous for an intravenous anti-infective (dichotomous)	MM diagnosis to 1 day prior to index date

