Antibiotics	Baseline characteristic - Treatments	Claims data	
HCPCS/CPT (Mapped via Athena – OHDSI using generic name): J0561, J0278, S0016, S0072, G9313, G9314, G9315, J0290, J0295, J0714, J0456, Q0144, J0688, 4041F, G8198, G8199, G8527, J0690, J0699, J0693, J0698, J0714, J0713, C9452, J0695, J0696, 4041F, G8198, G8199, G8527, J0697, J0720, J0742, J0743, C9479, J0744, J7342, S0024, J0736, S0077, J1364, J1362, J1580, J1956, J2021, J2020, C9001, J2184, J2185, J2186, J1836, S0030, J2281, J2280, J2543, S0081, C9039, J0291, J3320, J3000, S0039, C9452, J0695, J2543, J3090, C9446, S0039, J2186, J3372, J3371, 4047F, 4048F, G8152, G8191, G8192, G8195, G8197, G8503, G8504, J3370, G8630, G8629
 
Generic names* (mapped to NDC codes via First Data Bank): Benzylpenicillin, Cefalexin, Cloxacillin, Doxycycline, Nitrofurantoin, Phenoxyimethylpenicillin, Cefixime, Colistin, Fosfomycin, Clofazimine, Dapsone, Rifampicin, Ethambutol, Isoniazid, Pyrazinamide, Rifapentine, Bedaquiline, Cycloserine, Terizidone, Protonamide, Imipenem, P-Aminosalicylate, Pretomanid, Amikacin, Amoxicillin, Ampicillin, Avibactam,
	WHO (2023) Athena – OHDSI

			
Azithromycin, Cefazolin, Cefiderocol, Cefotaxime, Ceftazidime, Ceftolozane, Ceftriaxone, Cefuroxime, Chloramphenicol, Cilastatin, Ciprofloxacin, Clarithromycin, Clindamycin, Delamanid, Erythromycin, Ethionamide, Gentamicin, Levofloxacin, Linezolid, Meropenem, Metronidazole, Moxifloxacin, Piperacillin, Plazomicin, Polymyxin, Spectinomycin, Streptomycin, Sulfamethoxazole, Tazobactam, Tedizolid, Trimethoprim, Vaborbactam, Vancomycin, Rifabutin
 
*Therapies in combination with any of the listed generic names will be included
	
Antifungals	Baseline characteristic - Treatments	Claims data	
HCPCS (Mapped via Athena – OHDSI using generic name): J0285, J0287, J0288, J0289, J0286, K0453, J1450, S0029, J1835, S0096, J2247, C9227, J2248, J3465, J0637, C9019, J0348
 
Generic name* (mapped to NDC codes via First Data Bank): Amphotericin B, Clotrimazole, Fluconazole, Flucytosine, Griseofulvin, Itraconazole, Nystatin, Voriconazole, Micafungin, Caspofungin, Anidulafungin
 
*Therapies in combination with any of the listed generic names will be included
	
WHO (2023) Athena – OHDSI

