Intravenous immunoglobulin	Baseline characteristic - Treatments, Dexamethasone	Claims data	
HCPCS (Mapped via Athena – OHDSI using brand name): J1556, C9130, J1557, J1559, C9270, Q4097, Q4092, Q4091, Q4088, Q4087, J1572, J1569, J1568, J1562, J1459, J1576, J1555, C9072, J1551, J1554, J1558
 
Brand Name (mapped to NDC codes via First Data Bank): Asceniv, Bivigam, Gammagplex, Privigen, Octagam, Flebogamma/Flebogamma Dif, Panzyga, Gammagard Liquid, Flebogamma, Gamunex, Gammagard N, LAndoglobulin, Polygam S/D, Gammagard S-D, Gammagard S/D, Gammagard,
	
Mayo Clinic (2024) Athena – OHDSI

			Panglobulin, Carimune, Carimune Nf Nanofiltered, Venoglobulin-S, Iveegam En, Flebogamma Dif	
Other hematological malignancies	Baseline characteristic - Clinical	Claims data	ICD-10 Diagnosis: Lymphoma; malignant plasma cell neoplasm; leukemia; other and unspecified malignant neoplasms of lymphoid, hematopoietic, and related tissue; and myelodysplastic syndrome: C81-C96, D46 (Excluding C90.0x)	Maziarz et al. (2024)
Any non-hematological malignancy	Baseline characteristic - Clinical	Claims data	ICD-10 Diagnosis: C0x.x, C1x.x, C2x.x, C30.x, C31.x, C32.x, C33.x, C34.x, C37.x, C38.x, C39.x, C40.x, C41.x, C43.x, C45.x, C46.x, C47.x, C48.x, C49.x, C50, C51-C58.x, C60-63.x, C76.x, C80.1	Glasheen et al. (2019)
Plasma cell leukemia	Baseline characteristic - Clinical	Claims data	ICD-10 Diagnosis: C90.1x	Wu et al. (2017)
Graft vs host disease	Baseline characteristic - Clinical	Claims data	ICD-10 Diagnosis: D89.81x	Huang et al. (2023)
Benign bone lesions	Baseline characteristic - Clinical	Claims data	ICD-10 Diagnosis: D16.0-D16.9, M85.0, M85.4-M85.6, D48.0	Muran et al. (2023)
Peripheral neuropathy	Baseline characteristic - Clinical, AE	Claims data	ICD-10 Diagnosis: G90.50, G90.513, G90.511, G90.512, G90.519, G90.521, G90.529, G90.522, G90.523, G90.59, G54.0, G55, G54.2, G54.4, E08.41, E09.41, E10.41, E11.41, E13.41, G57.70, G57.71, G57.72, G57.73, G59, G57.80, G57.81, G57.82, G57.83, G58.8, G58.9, G64, G61.0, M05.50, M05.511, M05.512, M05.519, M05.521, M05.522, M05.529, M05.531, M05.532, M05.539, M05.541, M05.542, M05.549, M05.551, M05.552, M05.559, M05.561, M05.562, M05.569, M05.571, M05.572, M05.579, M05.59, E08.40, E08.42, E09.40, E09.42, E10.40, E10.42, E11.40, E11.42, E13.40, E13.42, G13.0, G13.1, A36.83, A52.15, G63, M34.83, G62.1, G61.1, G62.0, G62.2, G62.82, G61.81, G62.81, G61.89,	Song et al. (2019)

PFIZER CONFIDENTIAL

Redacted

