			G62.89, G61.9, G62.9, H46.3, M54.10, M54.18, M79.2, R20.0, R20.1, R20.2, R20.3, R20.8, R20.9	
Any infection	Baseline characteristic - Clinical	Claims data	An ICD-10 Diagnosis Code for any of the following types of infections. See the rows below for codes for each infection type. COVID-19, Adenoviral pneumonia, Cytomegaloviral pneumonitis, Other Pneumonia, Upper respiratory tract infection, Sepsis, Cytomegaloviral infection, PJP, Hepatitis C, Hepatitis B, Other infectious hepatitis, Helicobacter pylori, Candida esophagitis, Urinary tract infection	N/A
Use of intravenous anti-infective	Baseline characteristic - Clinical	Claims data	See “Antivirals,” “Antibiotics,” and “Antifungals” and where service category = injection/infusion drugs or where route = injectable or route array has injectable in it OR HCPCS/CPT codes that indicate IV administration of an anti-infective	N/A
Absolute neutrophil count (for Neutropenia)	Baseline characteristic - Clinical, AE	Claims data	White blood cell count x the percentage of neutrophils White blood cell count: Results_value in the lab results table where the result_abbrev is wbc and result_units are thousand per μ L Percent Neutrophil: Results_value in the lab results table where the result_abbrev is neutrophils percent and result_units are percent White blood cell count and percent neutrophil results must occur on the same day	Severe Chronic Neutropenia International Registry
Neutropenia	Baseline characteristic - Clinical, AE	Claims data	ICD-10 Diagnosis: D70.x or Absolute neutrophil count < 1500 cells per μ L	Kim et al. (2022) Lustberg et al. (2012)

PFIZER CONFIDENTIAL

Redacted

Hypercalcemia	Baseline characteristic - Clinical	Claims data	ICD-10 Diagnosis: E83.52 or value in the GDD table where test is hypercalcemia and result_units are mg/dL and result_value is > 11.5	Kumi et al. (2024) CTCAE v6 (2020)
Hepatotoxicity	Baseline characteristic - Clinical, AE	Claims data	ICD-10 Diagnosis: K71.x	Banerjee et al. (2023)
Amyloidosis	Baseline characteristic - Clinical	Claims data	ICD-10 Diagnosis: E85.4x, E85.8x, E85.9x	Quock et al. (2018)
Hypertension	Baseline characteristic - Clinical	Claims data	ICD-10 Diagnosis: I10x-I15x	Angier et al. (2019)
Extramedullary plasmacytoma	Baseline characteristic - Clinical	Claims data	ICD-10 Diagnosis: C90.2x	Ellington et al. (2021)
CCI score	Baseline characteristic - Clinical	Claims data	See components below	Glasheen et al. (2019)

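### The Annex 2 antibiotic and antifungal lists are closed name lists that omit common systemic agents and set no route limit, so the descriptive anti-infective percentages are misclassified

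*Protocol*

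**What the plan says.** Section 9.3, Table 2, defines the antibiotic variable as "Medical claim with an NDC, HCPCS, generic name or CPT code in the IP, non-IP, or pharmacy setting for antibiotic medications (dichotomous". The antifungal row has the same form: a claim "in the IP, non-IP, or pharmacy setting for antifungal medications (dichotomous". Both are assessed from 14 days to 1 day before index and again from index to the end of follow-up. Section 9.3 refers to Annex 2 for the full code list.

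Annex 2 gives each variable a fixed set of generic names, cites WHO (2023) as the source, and expands the names to NDC codes through a commercial drug file. The antifungal names are "Amphotericin B, Clotrimazole, Fluconazole, Flucytosine, Griseofulvin, Itraconazole, Nystatin, Voriconazole, Micafungin, Caspofungin, Anidulafungin". The antibiotic names include the runs "Benzylpenicillin, Cefalexin, Cloxacillin, Doxycycline" and "Azithromycin, Cefazolin, Cefiderocol, Cefotaxime, Ceftazidime, Ceftolozane, Ceftriaxone, Cefuroxime". In both rows the procedure codes are stated to be mapped using the generic name. A footnote adds combination products that contain a listed name.

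A route condition appears only in a separate Annex 2 row, Use of intravenous anti-infective. That row takes the antiviral, antibiotic and antifungal lists "where service category = injection/infusion drugs" or where the route is injectable. It then adds, as an alternative, HCPCS/CPT codes indicating intravenous administration of an anti-infective, without listing them.

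**The concern.** Table 2 names two drug classes, and Annex 2 delivers a selection from each. A reader of the results will take the percentage with antibiotic or antifungal use as class-wide use. Two errors act on it in opposite directions. Patients whose only agents are unlisted systemic drugs are recorded as non-users. Patients whose only claim is a cream, an eye or ear product or another non-systemic form of a listed drug are recorded as users.

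At stake is the description of anti-infective treatment under primary Objective 1, before and during treatment, in the elranatamab cohort and in the exploratory teclistamab cohort. Section 9.8 says that the protocol's codes and algorithms will be strictly followed, so the analyst has no stated freedom to complete the lists. Section 9.9 does not mention the limitation.

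**Working it through.** The plan states no figure to reproduce. The check compares the definition with the list.

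**1. Membership.** The antibiotic row holds 61 distinct names and the antifungal row 11. Ten systemic agents were looked up:

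| Drug | Class row | On the list? |
|---|---|---|
| cefepime, ertapenem, daptomycin | Antibiotics | No |
| aztreonam, tobramycin, minocycline | Antibiotics | No |
| cefdinir, cefpodoxime | Antibiotics | No |
| posaconazole, isavuconazole | Antifungals | No |

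That these ten drugs are systemic antibacterials or antifungals is general drug knowledge. Their absence is read from Annex 2.

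**2. Could another part of the row capture them?** The procedure codes (82 antibiotic entries, 72 of them distinct, and 17 antifungal entries) are stated to be mapped from the generic names. A drug that is not named therefore has no mapped code. The combination footnote adds only products that contain a listed name, and none of the ten does so as a single agent.

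**3. Route.** Table 2 specifies the claim setting (inpatient, non-inpatient, pharmacy) but no route. Annex 2 expands each name to NDC codes without a route condition. Clotrimazole and nystatin are on the antifungal list; erythromycin, gentamicin and ciprofloxacin are on the antibiotic list. That these are also sold in topical, eye or ear forms is general knowledge; the documents show only that nothing excludes such forms. The intravenous anti-infective row shows that a route field is available in the data.

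**4. Direction.** Let p be the true proportion with systemic use in the window, s the share of those users with at least one listed agent, and f the share of non-users with only a non-systemic claim. Then

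reported = p × s + (1 − p) × f.

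The protocol gives none of the three. The values below are assumptions chosen only to show that the sign is open:

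- p = 0.20, s = 0.60, f = 0: 0.20 × 0.60 + 0.80 × 0 = 12.0%
- p = 0.20, s = 0.80, f = 0.05: 0.16 + 0.04 = 20.0%, so the two errors cancel
- p = 0.20, s = 0.95, f = 0.05: 0.19 + 0.04 = 23.0%

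With a true value of 20%, the reported value can fall below it, on it or above it.

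**The case against.** The strongest reply is that Annex 2 is itself the operational definition. Table 2 says neither any nor systemic, and where the authors wanted a route limit they wrote one. On that reading nothing is contradicted. This stands in part: restricting to systemic routes is a choice the authors may make or decline. But the variables carry class names, and a list without the drugs above does not measure the class. The text also leaves open which routes are meant.

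A second reply concerns size, and it stands. Each variable is yes/no per patient, so a patient is lost only if every agent in the window is unlisted. The lists do contain vancomycin, piperacillin, meropenem, ceftriaxone, levofloxacin, sulfamethoxazole, trimethoprim, fluconazole, voriconazole and three echinocandins. Annex 2 gives the two rows only a baseline-treatment role, without the resource-use role given to the myeloma drugs.

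A reader might go further in four ways that the documents do not support:

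- **Intravenous cefepime or daptomycin is missed by the intravenous anti-infective variable.** Its open alternative arm of HCPCS/CPT codes could catch both. Because the codes are not listed, capture can be neither confirmed nor denied. The injectable condition also keeps creams and drops out of the list-based arm.
- **The infection adverse-event rates are affected.** Those events are defined by ICD-10 diagnosis codes, not by drug claims.
- **International names such as those in "Benzylpenicillin, Cefalexin, Cloxacillin, Doxycycline" fail to map in a US drug file.** The mapping step is not shown, so this is conjecture.
- **The intravenous immunoglobulin row contains the wrong codes.** The protocol does not say which product or route each code denotes, and that row also captures by brand name.

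**Conclusion.** The point holds for the Antibiotics and Antifungals variables: the lists are incomplete for the classes they name, and non-systemic forms count as use. The resulting percentages are misclassified at baseline and in follow-up in both cohorts. Neither size nor net direction can be computed from the documents, so a statement that use is under-reported would go too far. The conclusion rests on reading the class labels in Table 2 as class-wide use and on general knowledge of which drugs are systemic and which have topical forms.

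Severity is minor. These are descriptive variables; no test, sample size, adverse-event definition, TTD, TTNT/D, OS or MM-related resource-use or cost measure depends on them.

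**What to change.** - State in Table 2 that the two variables mean systemic use.
- Build both lists by drug class: all systemic antibacterials and all systemic antifungals in the drug file, with their HCPCS codes.
- Restrict them to oral and parenteral routes, using the route field already applied in the intravenous anti-infective row.
- Use the rebuilt lists for Use of intravenous anti-infective, and list the codes in its open HCPCS/CPT arm.

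The cost is one code-list rebuild and a rerun. Earlier refreshes must be rerun to stay comparable. Version 2.0 is dated 31 July 2025, ahead of refresh 3 (09 September 2025), refresh 4 (20 December 2025) and the final report (28 February 2026). If the lists are kept as they are, the variables should be relabelled as use of listed agents by any route, and the limitation stated in Section 9.9.
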